**Figure 1: Study Design**

Subjects who discontinue study drug(s) early are encouraged to stay in the study for continued safety monitoring which begins at EOT and ends 7 months after randomization. The data collected after treatment discontinuation will include all efficacy assessments (in addition to safety) as for those who continue randomized therapy.

## 4.2. Treatment, Route, Dosage, Treatment Period

Eligible subjects with non-cavitary lung disease with new (initial or subsequent) MAC lung infections who have not started treatment for their current infection and who have signed the ICFs will be randomized and will receive treatment as follows:

- ALIS 590 mg QD + AZI 250 mg QD + ETH 15 mg/kg QD for 6 months, or
- ELC (matching placebo for ALIS) + AZI 250 mg QD + ETH 15 mg/kg QD for 6 months

### Treatment

In this study, the term "treatment" or "treatment group" designates the randomization arm to which a subject is assigned, i.e., either ALIS + AZI + ETH or ELC + AZI + ETH.

### Treatment Period

The treatment period starts with the first dose of ALIS/ELC, AZI and/or ETH.

The end of treatment (EOT) is defined as the date of the last dose of ALIS/ELC, AZI and/or ETH whichever study drug dose is taken last.

## 4.3. Sample Size Determination

### 4.3.1. Power and Sample Size Determination for the Validation Study

Cross-sectional validation will require baseline data from a maximum of 250 subjects to adequately power the planned MPMs. A total of 100 subjects will be enrolled in this study and will be used for this analysis. Additional baseline data from up to the first 150 subjects enrolled in INS-416 study will be used.

Longitudinal validation will require 100 subjects to adequately power the planned within-subject meaningful change methods.

The derivation of these sample sizes and the procedures used to compute power are described below.

### Cross-sectional Validation Power and Sample Size

The estimated sample size required to conduct cross-sectional validation of the PRO endpoints within the NTM-MAC population was obtained from a power analysis assuming the PRO will be composed of 10 total items analyzed with 5 response categories each. This power procedure determines the sample size required to detect a domain specification that fits the data acceptably well ([Serrano and Iaconangelo, 2019\[10\]](#); [Serrano and Iaconangelo, 2017\[11\]](#)). The model fit statistic for which power was computed is the RMSEA. The RMSEA is the primary fit index used in modern psychometric methods for determining the optimal domain structure. This fit assessment is the logical test to power, as the modern psychometric methods require the largest sample sizes of all validation analyses. Therefore, adequately powering modern psychometric methods is key to validation study success. In addition, the precision of all validation analyses subsequent to modern psychometric methods rely on correct domain specification, which itself relies on the RMSEA.

For a 10-item questionnaire, approximately  $n=250$  is required to achieve a power of 0.80 for the RMSEA-based test of acceptable MPM model fit. Therefore, a maximum of 250

subjects are planned for the study cross-sectional validation analyses. These subjects will contribute data at both Screening and Baseline for the purposes of estimated test-retest reliability as well. Longitudinal validation analyses will be conducted on the subset of 100 subjects enrolled into this study.

### **Longitudinal Validation Power and Sample Size**

An empirical power analysis simulation was conducted to evaluate the optimal sample size to adequately characterize culture converter anchor-based within-subject meaningful change in this study.

Inputs to the power analysis simulations were obtained from the MAC subset of the ALIS treated subjects in Insmmed Study TR02-112, and simulation conditions considered reflected conservative variation around observed estimates (larger dispersion and smaller magnitudes of effect). The following conditions were used to compute power: magnitudes of effect in change from baseline (6pt, 7pt, 8pt, 9pt, and 12pt change from baseline in converters, and 3 point change from baseline in non-converters); culture converter proportions (50%, 60%, and 70%); proportion data missing at random (MAR, 0%, 5%, 20%, 25%, and 30%); and sample size (n=100, n=120, and n=130). The polyserial correlation between simulated change from baseline in QOL-B respiratory domain and culture conversion varied around the observed estimate of 0.47, ranging from 0.3 to 0.6. Within each unique simulation condition r=1000 replications were generated. Empirical power was computed as the number of replications for which statistically significant differences between converters and non-converters in change from baseline in QOL-B respiratory domain score were observed. For example, if 900 replications demonstrated significant differences using the 2-sided test conducted at  $\alpha=0.05$ , then power was 90%.

A total sample size of 100 subjects (50 subjects per treatment arm) will provide at least 80% power for detecting 7 points mean difference in QOL-B respiratory domain response at 1-month post-treatment between subjects achieving culture conversion during the study and those who did not via ANOVA testing. This derivation assumes 50%, 60%, or 70% culture conversion rate, at least 40% polyserial correlation between culture conversion and QOL-B respiratory domain response, and missing data of 0%, 5%, or 20%.

## **4.4. Randomization**

Upon meeting all inclusion/exclusion criteria at baseline visit, subjects will be randomly assigned through IWRS in a 1:1 ratio to either of the treatment groups. The randomization will be stratified by region (North America, Europe, and Rest of World) and history of MAC lung infection (initial or subsequent). Subjects, Investigators, and the Sponsor will be blinded to treatment group assignments and microbiology results throughout the study. In case of subject emergencies, unblinding of the assigned treatment will occur per established procedure.

## 5. PLANNED ANALYSES

### 5.1. Validation Analysis

The methods for validation analyses are described in the VAP. The results will be reported separately within the Validation Analysis Report.

Validation analysis include the following:

1. Scoring: Cross-sectional validation (modern psychometrics, internal consistency, concurrent validity, and known-groups validity) at Baseline.
2. Reliability and validity of scores: Test-retest reliability between Screening and Baseline among subjects reporting no change on PGI-S between screening and baseline. PGI-S anchors will be PRO specific, with a respiratory and fatigue PGI-S applied to the QOL-B respiratory domain and PROMIS F-SF 7a, respectively.
3. Responsiveness: Longitudinal analysis - Within-subject meaningful change estimated via anchor-based methods and validated via eCDFs and ePDFs between Baseline and EOS (Month 7).

The analyses for Scoring, Reliability, and Responsiveness require Screening and Baseline data from up to a maximum of 250 subjects (100 subjects from INS-415 study and the first enrolled 150 subjects from INS-416 study). This sample size allows for initiation of RMSEA-based model fit testing with baseline data only (blinded to randomized study groups) from less than 250 subjects; therefore, an attempt will be made when 180 and/or 230 subjects will be enrolled in this study and INS-416 combined. Only if RMSEA-based model fit power testing demonstrates good model fit would cross-sectional validation then proceed. If testing does not indicate good fit at 180 or 230 it would be re-evaluated when 250 subjects are enrolled, which is the maximum planned for cross-sectional validation. RMSEA-based testing ensures the analysis will be performed with sufficient power, voiding any significant impact on the scientific validity of the study. Further, the analysis does not require treatment group assignment, hence will be performed as soon as the data will be available and cleaned, ie, before the unblinding of the INS-415 study. Further details are included in VAP.

The longitudinal analysis requires observed post-baseline data, hence will be performed after data base lock and unblinding of the study.

### 5.2. Final Analysis

Final analysis is planned to be conducted after data base lock and unblinding of the study.

The final validated PRO instrument will be based on the QOL-B respiratory domain or PROMIS Fatigue but may or may not include all the items from the original scale. Should one or both scales change, certain analyses will be provided on this final PRO Instrument. The change in scales will be provided at the time of Validation Report; hence, the revised analyses if appropriate will be appended to the CSR.

If the number of items used in the PRO scores(s) is a subset of the complete set, the following endpoints and analyses may be revised:

**Table 2: List of Endpoints and analyses affected by scoring algorithm change**

Endpoint	Analysis	Analysis description included in SAP Section
Patient-reported respiratory symptoms at Month 7	Change from Baseline to Month 7 in respiratory symptom score	Section 9.3.2
	Summaries by timepoint	Section 9.3.2
	Within-subject meaningful change threshold estimated in respiratory symptoms from Baseline to Month 7	Section 10.3
	Subgroup analyses	Section 9.3.8
	Correlations	Section 11.4
Patient-reported fatigue symptoms at Month 7	Change from Baseline to Month 7 in fatigue symptom score	Section 9.3.3
	Summaries by timepoint	Section 9.3.3
	Within-subject meaningful change threshold estimated in respiratory symptoms from Baseline to Month 7	Section 10.3
	Subgroup analyses	Section 9.3.8
	Correlations	Section 11.4

### 5.3. DMC Monitoring Analysis

Periodic review of data for the purpose of safety will be conducted by the DMC; details are described in a separate DMC charter and DMC SAP, together with details regarding safety summaries and listings. DMC meetings will be held when approximately 25%, 50%, 75%, and 100% of total planned number of subjects in studies INS-415 and INS-416 are randomized. Subsequent meetings will be held approximately every 6 months until completion of the study.

## **6. ANALYSIS SETS**

### **6.1. ITT Analysis Sets**

The ITT analysis set comprises all subjects who were randomized. This set will be analyzed using the treatment to which the subject was randomized.

### **6.2. Safety Analysis Set**

The safety analysis set comprises all subjects who were randomized and received at least 1 dose of ALIS, ELC, AZI or ETH.

## 7. GENERAL STATISTICAL CONSIDERATIONS

### 7.1. General

All summaries will be provided by treatment group; efficacy analyses will utilize randomized treatment (ITT analysis set), while safety will use treatments as received (Safety analysis set).

In case of misrandomization to incorrect strata, subjects will be analyzed as collected in CRF.

Methods of cross-sectional analyses and psychometric validation of PRO are described in the VAP.

Descriptive statistics for continuous variables include n, mean, SD, median, minimum, maximum, 1st quartile and 3rd quartile. Summaries of continuous variables that have some values recorded using approximate values (eg, < or >) will use the numeric part of the value in calculations. Listings will present the data in its original format.

Categorical variables will be tabulated by counts and by percentage of subjects in corresponding categories. Footnotes will specify the basis for the percentages. Category including missing assessments will be included if appropriate.

Data from unscheduled visits will not be used in summaries, except for the derivation of baseline and the summary of subjects with an abnormal laboratory value.

Listings corresponding to all summaries in this section will be provided. Listings will also include data from unscheduled visits.

### 7.2. Multiple Comparisons and Multiplicity

All summaries presented within the scope of this SAP will be descriptive without multiplicity adjustment. Ninety-five percent confidence intervals for estimation of treatment differences and associated p-values will not be adjusted for multiplicity. There is no intention to make inferences based on these statistics, as their value is nominal.

### 7.3. Baseline Definition

Unless otherwise stated, for the purpose of analysis baseline value is the last non-missing value prior or at the date of the first dose of ALIS/ELC, AZI or ETH, regardless of the visit in which it occurs including unscheduled visits.

Change from baseline will be calculated as:

- Change from baseline = post baseline value – baseline value

Ratio from baseline will be calculated as:

- Ratio from baseline = post baseline value / baseline value

Many assessments are done at Screening and Baseline/Day 1. For summaries, whenever baseline is presented, the above baseline definition is used. That is, the baseline summary presented is in general not the summary of the Baseline/Day 1 visit. Screening values will be listed but not summarized.

Throughout the document Baseline (capital B) refers to the visit Baseline/Day 1; baseline (lower case b) refers to the values derived using the baseline definition above.

The baseline MAC species/genome is the species grown in sputum samples collected at Baseline/Day 1. If Baseline/Day 1 is MAC culture negative or missing, the Screening samples will be taken instead (see [Section 9.3.7.1](#)).

Subjects being evaluated in this study have a diagnosis of MAC lung disease, as indicated by an investigator-reported positive MAC culture within 6 months of Screening, and a single sputum sample that is positive for MAC culture at Screening. For the purpose of descriptive summaries at Baseline, if culture assessment is negative at the Baseline visit, the baseline culture status will be regarded as the value at the screening visit.

For the purpose of actigraphy data analysis, baseline will be defined as data recorded in the period Day 8 – Day 14.

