- c. Subjects will remain off all study drugs and should avoid initiating any new medical or non-medical therapies for MAC lung infection.
- d. Serum pregnancy testing will be performed on WOCBP at Screening. A urine pregnancy test (at least 25 mIU/mL sensitivity) must be performed for all WOCBP at all subsequent visits starting at Baseline. Women not of childbearing potential are defined as postmenopausal (ie, amenorrheic for at least 12 months), or surgically or naturally sterile.
- e. All PRO assessments will be performed prior to any other assessments (with the exception of sputum collection) and administration of study drugs and should be performed in the following order: QOL-B, PROMIS F-SF 7a, EXACT, EXACT-RS, SGRQ, FACIT-Fatigue, PGI-S-Respiratory, and PGI-S-Fatigue.
- f. Collection of data is continuous. Data will be retrieved by study staff at in-clinic visits.
- g. The physical examination will also include measurement of body weight; the measurement of height, without shoes, will only be done at Screening. All physical examinations should be performed prior to administration of study drugs.
- h. Vital signs and pulse oximetry will be assessed prior to administration of study drugs.
- i. The Baseline audiology examination must be performed during Screening or on Day 1 before administration of study drugs and evaluated by the Investigator.
- j. Tests may be performed if required by local labeling guidance; Investigators should perform all monitoring according to local label
- k. Only SAEs will be collected after the ICF is signed until Baseline.
- l. At Baseline, AEs will be assessed only after administration of study drugs. Any AE that has occurred prior to the first dose must be included in the subject's medical history, including any AEs that occur within the Screening period.

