10.7.4. Clinical Laboratory Evaluation Analyses

The results of hematology, blood chemistry, and urinalysis will be tabulated by treatment group. Laboratory values outside the normal ranges will be flagged. Subjects experiencing ALT or AST $\geq 3^*$ ULN and total bilirubin $> 2^*$ ULN according to Hy's Law will be listed.

Summary statistics (mean, median, range, change from Baseline) by treatment will be provided for each timepoint, as appropriate.

Baseline value is defined by laboratory results collected prior to first study drugs administration.

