10.7.5. Vital Sign Analyses

Systolic and diastolic BP, pulse rate, RR, oxygen saturation, and body temperature will be listed for each subject. If applicable, summary statistics (mean change, percentage change from Baseline, and absolute change from Baseline) by treatment at each time point will be provided. Baseline value is defined as vital signs collected prior to the first dose of study drugs on Day 1/Baseline.

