## 2. INTRODUCTION

The purpose of this SAP is to describe the planned analyses to be included in the CSR for study INS-415.

The reader is encouraged to read the study protocol for details on the conduct of this study, the operational aspects of clinical assessments, and the timing for a subject to complete participation in this study.

The SAP is intended to be in agreement with the protocol. However, the SAP may contain more details or other types of analyses (eg, other endpoints). When differences exist in descriptions or explanations provided in the study protocol and this SAP, the SAP prevails; the differences will be explained in the CSR.

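### SAP 7.3 sets baseline by the date of first dose and admits unscheduled records, so a post-dose Day 1 reading can become a safety baseline; this departs from the protocol and is not listed in SAP Table 9 (minor)

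*SAP*

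**What the plan says.** SAP 7.3 gives a general rule, applied unless another is stated: baseline is the "last non-missing value prior or at the date of the first dose of ALIS/ELC, AZI or ETH", and this holds "regardless of the visit in which it occurs including unscheduled visits". The cut-off is a calendar date, with no time-of-day or pre-dose condition. SAP 12.9 (laboratory) and 12.10 (vital signs) both use change from baseline, and neither states a different rule.

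The protocol does set a pre-dose condition. For laboratory values (10.7.4): "Baseline value is defined by laboratory results collected prior to first study drugs administration". For vital signs (10.7.5): "Baseline value is defined as vital signs collected prior to the first dose of study drugs on Day 1/Baseline".

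SAP 7.1 adds: "Data from unscheduled visits will not be used in summaries, except for the derivation of baseline". The same sentence makes a second exception, for the summary of subjects with an abnormal laboratory value.

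On precedence, SAP section 2 says: "When differences exist in descriptions or explanations provided in the study protocol and this SAP, the SAP prevails". SAP Table 9, which records changes to protocol-specified analyses, has one entry, the end-of-treatment definition.

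**The concern.** A baseline for safety change scores should precede exposure. The SAP wording allows one that does not. If a subject is dosed on Day 1 and measured again later that day at an unscheduled assessment, the later value is the last one on the date of first dose and so meets the SAP definition. The protocol's definition would exclude it. Because the SAP prevails and the difference is not declared, a programmer following the SAP would use the post-dose value.

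At stake are that subject's later changes from baseline in vital signs and laboratory values and, for laboratory tests, the starting category in the low/normal/high shift table. Safety and tolerability is a secondary objective, and its endpoint names both kinds of measurement.

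**Working it through.** The plan states no figure on this point, so the check traces the text and adds one illustration.

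1. **Scheduled Day 1 values.** Protocol Table 4, footnote h: "Vital signs and pulse oximetry will be assessed prior to administration of study drugs". Footnote n puts laboratory tests before dosing, and protocol 5.1.4 makes ALIS/ELC administration the last procedure on a visit day. If the protocol is followed, scheduled values give a pre-dose baseline under either rule.

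2. **Unscheduled values on Day 1.** Protocol 6.1 foresees unscheduled assessments when local labeling recommends extra monitoring. Footnote l of Table 4 reads: "At Baseline, AEs will be assessed only after administration of study drugs". Subjects are therefore under observation after dosing, although that footnote schedules no measurement. A post-dose reading on that date is possible but not planned.

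3. **Vital signs and oximetry.** Such a reading is the last on the date of first dose and becomes baseline. Under SAP 7.1 it enters the summaries only in that role.

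4. **Laboratory values.** Two SAP rules compete. Under 7.3 the later value replaces the pre-dose one. Under 7.6.4, multiple numeric laboratory records at one visit or timepoint are averaged, and a central result is used over a local one. The SAP does not say which section applies first. With two records a (pre-dose) and b (post-dose), the baseline error is b − a under 7.3 and (a + b)/2 − a = (b − a)/2 under averaging. Averaging halves the error but does not remove it.

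5. **Other outcomes.** PROs are completed before dosing (footnote e), baseline audiology must be done at Screening or before dosing on Day 1 (footnote i), and Day 1 FEV1 precedes dosing (protocol 9.4). Actigraphy has its own baseline window in SAP 7.3. No efficacy PRO result is shown to be affected.

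6. **Illustration (all readings assumed).** Oxygen saturation is 96% before dosing, 88% at an unscheduled post-dose reading on Day 1, and 95% at Month 1.
   - Pre-dose baseline: 95 − 96 = −1.
   - SAP 7.3 baseline: 95 − 88 = +7.
   - Difference d = 7 − (−1) = 8 points, with the sign reversed.

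7. **Effect on an arm mean.** The shift is k × d / n, where k is the number of affected subjects and n = 50 per arm (SAP 4.3.1). With d = 8:
   - k = 1: 1 × 8 / 50 = 0.16 points.
   - k = 5: 5 × 8 / 50 = 0.80 points.
   - k = 10: 10 × 8 / 50 = 1.60 points.

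   The documents give no value for k, and it could be zero.

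**The case against.** The strongest reply is that the trigger is rare and the consequence narrow. Every scheduled Day 1 assessment is pre-dose, and no passage says that a subject who reacts will be re-measured the same day. The summaries are descriptive with no inference intended (SAP 7.2), and the primary objective is psychometric validation. This stands, and it is why the point is minor.

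A reader might infer that the rule hides first-dose reactions. The documents do not support that. A reported event on the date of first dose is a TEAE (SAP 12.4) and enters the special-interest tables if its preferred term qualifies. Listings include unscheduled values (SAP 7.1), and unscheduled abnormal laboratory values are counted (SAP 12.9). There are limits: SAP 12.10 plans no similar count for vital signs, and protocol 9.9.2 makes an abnormal value an adverse event only under conditions such as associated symptoms or investigator-judged significance.

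A reader might also infer a bias in favour of ALIS. Protocol 9.9.6 associates ALIS with respiratory symptoms and says that most ALIS-treated subjects in the earlier refractory-disease study had their first adverse event within 60 days. It says nothing about Day 1. The cited signal is also respiratory, whereas shift tables are planned only for laboratory values. A tilt between arms is conjecture.

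Finally, a timing condition might seem to need clock times that the documents do not say are captured. The fix below does not depend on them.

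**Conclusion.** The SAP baseline rule is wrong as written, with minor severity. It can admit a post-exposure value, it conflicts with protocol 10.7.4 and 10.7.5, and the change is not declared in Table 9. The effect is confined to vital-sign and laboratory baseline summaries, changes from baseline and laboratory shift categories, and only for subjects with an unscheduled or out-of-order reading after dosing on Day 1.

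For such a subject the error can be large enough to reverse the sign of a change. For an arm mean it is small, at 0.16 points per affected subject under the assumed 8-point difference and 50 per arm. The number affected is not given and is probably small. Neither concealment of reactions nor a direction of bias between arms is established.

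**What to change.** Reword SAP 7.3 so that baseline is the last non-missing value before the first dose of any study drug. Add three clauses:

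- On the date of first dose, use the scheduled Baseline/Day 1 assessment, which Table 4 requires to be pre-dose, unless it is documented as taken after dosing.
- Exclude same-day unscheduled records unless they are documented as pre-dose. Missing clock times then lead to exclusion rather than ambiguity.
- State that this rule takes precedence over the averaging in SAP 7.6.4.

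The cost is a few lines of SAP text and one condition in the baseline derivation, with no new data collection. It restores the protocol's definition, so no Table 9 entry is needed. If the date-based rule is kept, it should be listed and justified there. The change corrects later changes from baseline; it does not bring the acute Day 1 reading into the by-visit summaries, where unscheduled data remain excluded.
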